	# expected		
	Post-Amendment 3:		
	100 × # of sachets taken		
	# expected		

¹ Study part refers to pre-amendment 3 and post-amendment 3; pre-amendment 3 has both open-label and double-blind periods, post-amendment 3 has only open-label period.

5.1.1.4.2 Adverse Events

Adverse event summaries will be presented for each safety population as follows:

- Post-Amendment 3 open-label safety population: by oxybutynin chloride gel dose level and overall
- Pre-Amendment 3 double-blind safety population: by treatment group, treatment and dose level, and overall
- Pre-Amendment 3 open-label safety population: by oxybutynin chloride gel dose level and overall
- Combined open-label safety population: by oxybutynin chloride gel dose level and overall

Adverse event summaries will be done overall and also for each age, weight, and sex group.

The following adverse event (AE) terms are defined:

An AE will be considered as a treatment-emergent adverse event (TEAE) if the AE initially occurs or increases in intensity on or after the first dose of study drug in the study. An event that occurs more than 30 days after the last dose of study drug will not be considered as treatment-emergent.

Table 5-15 AE Terms

Term	Description
Treatment- emergent	Double-blind period:
emergene	 First dose date of double-blind period ≤ event start date ≤ last dose date of double-blind period + 30 days if participant does not enter the 8-week open-label period; or First dose date of double-blind period ≤ event start date < first dose date of open-label period if participant enters the 8-week open-label period
	 Open-label period: First start date of open-label period ≤ event start date ≤ last dose date of open-label period + 30 days

AEs, encompassing abnormalities and surgeries reported as occurring after the Screening Visit, will be coded using MedDRA Version 19.1 or later. Unique participants reporting AEs in the following AE categories will be summarized for the groups defined above for each safety population as follows:

[figure not shown]

Table 5-16 AE Summaries

Parameter	Description	Timing	Methodology
Overall summary	Overall summary only for the following category: • Treatment-emergent AEs (TEAEs)	Study Period within Study Part ^{2,3} ; Combined open-label period	Categorical descriptives
TEAE	Overall summary and by SOC and PT	Study Period within Study Part ^{2,3} ; Combined open-label period	Categorical descriptives
TEAEs by severity	Overall summary and by SOC, PT, and intensity • Participants categorized overall and within each SOC and PT for the most intense occurrence	Study Period within Study Part ^{2,3} ; Combined open-label period	Categorical descriptives
TEAE by study treatment relationship	Overall summary and by SOC, PT, and study treatment relationship in descending order	Study Period within Study Part ^{2,3} ; Combined open-label period	Categorical descriptives
Serious TEAEs by study treatment relationship and severity	Overall summary and by SOC, PT, study treatment relationship and intensity • Participants categorized overall and within each SOC and PT for the most intense occurrence	Study Period within Study Part ^{2,3} ; Combined open-label period	Categorical descriptives
TEAEs leading to premature discontinuation ¹	Overall summary and by SOC, PT and study treatment relationship	Study Period within Study Part ^{2,3} ; Combined open-label period	Categorical descriptives

¹ Participants who report ≥ 1 AE in the AE category and all AEs for those participants will be listed. SOCs will be sorted alphabetically; PTs will be sorted in descending frequency in the highest dose group.

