9.4 Study Treatments

9.4.1 Treatments Administered

Pre-Amendment 3, patients were randomized to receive oxybutynin chloride gel or placebo during the 6-week double-blind treatment period, and all patients received oxybutynin chloride gel during the 8-week open-label treatment period. Patients randomized to double- blind oxybutynin chloride gel started treatment at 0.75 g/day, and the dose may have been adjusted after 2 weeks of treatment to a higher or lower dose (0.5 g/day or 1 g/day) based on the investigator's clinical judgment and assessment of bladder symptoms and treatment side effects. All patients who entered the open-label safety period were started on 0.75 g/day oxybutynin chloride gel, and the dose may have been adjusted after 2 weeks of treatment as described for the double-blind treatment period.

Post-Amendment 3, no changes were made in the starting dose, compared to the Pre-Amendment 3 study design, in that all patients will begin treatment with 0.75 g of gel/day for 2 weeks. Patients will then return to the clinic for a potential dose titration and at this time their dose may be adjusted up to 1 g/day, down to 0.5 g/day, or remain the same at 0.75 g/day, depending on individual response and tolerability. The determination of dose will be based on the investigator's clinical judgment and assessment of the patient's bladder symptoms and treatment side effects. Dose titration will be permitted only once during the entire 14-week treatment period. Patients will continue the adjusted dose for 12 additional weeks until the end of the open-label treatment period. *Patients* or parents/*caregiver* will apply the gel each morning to rotating application sites on the abdomen, upper arms/shoulders, and thighs. The person who applies the gel should wash *his or her* hands immediately after application with soap and water.

Patients should not bathe or shower sooner than 1 hour following a gel application. In the event of direct contact between unwashed or unclothed skin to which gel has been applied and the skin of another person, the contact area on the other person should be washed with soap and water as soon as possible.

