11.6.1 Adverse Events

Key results will be presented for each safety population as follows:

- Post-Amendment 3 open-label safety population: by oxybutynin chloride gel dose level and/or overall
- Pre-Amendment 3 double-blind safety population: by treatment group and/or treatment and dose level, and/or overall
- Pre-Amendment 3 open-label safety population: by treatment group in the lead-in double-blind period and overall
- Combined open-label safety population: by oxybutynin chloride gel dose level and/or overall

The incidence of treatment-emergent adverse events will be summarized for the safety populations *as described above*. Adverse events will be coded using Medical Dictionary for Regulatory Activities (MedDRA) terminology. Summaries of the following types will be provided:

- Overall summary of treatment-emergent adverse events
- Summary of treatment-emergent adverse events by MedDRA system organ class, MedDRA preferred term, *study treatment* relationship, and *severity*
- Summary of serious treatment-emergent adverse events by MedDRA system organ class, MedDRA preferred term, *study treatment* relationship, and *severity*
- Summary of treatment-emergent adverse events by MedDRA preferred term and *study treatment* relationship in descending order
- Summary of treatment-emergent adverse events by MedDRA system organ class, MedDRA preferred term, and *study treatment* relationship for events leading to premature discontinuation from the study

These summaries will present the number and percentage of *patients* reporting an adverse event for each classification level as well as the number of events reported. The denominators for calculating the percentages will be based on the number of *patients* in *each* safety population for each *tabulated* group.

All adverse events, *SAEs*, deaths, *SAEs* considered to be related to treatment, and adverse events leading to premature discontinuation from the study will also be provided in data listings.

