5.1.1.4.3 Clinical Laboratory Assessments

Clinical laboratory assessments will be summarized by treatment group, double-blind treatment/oxybutynin chloride gel sequence, or oxybutynin chloride gel only group, as applicable, and by analyte and visit for each safety population. Study Part is either Pre-Amendment 3 or Post-Amendment 3.

² Study part refers to pre-amendment 3 and post-amendment 3; pre-amendment 3 has both open-label and double-blind periods, post-amendment 3 has only open-label period.

³ AEs with onset more than 30 days after the last dose of study drug are excluded from analysis.

Table 5-17 Clinical Laboratory Summaries

Endpoint	Description	Timing	Methodology
Descriptives	Summary of change from baseline by laboratory	Visit F ¹ for Post-	CFB
	category and parameter in SI units and analysis	Amendment 3 and	descriptives
	visit	Visit 8 for Pre-	
	 Parameters specified in Section 6.4.2.2 	Amendment 3	
Descriptives	Summary of raw values by laboratory category	Visits A and F ¹	Continuous
	and parameter in SI units and analysis visit	for Post-	descriptives
	 Parameters specified in Section 6.4.2.2 	Amendment 3 and	
	-	Visits 1 and 8 for	
		Pre-Amendment 3	
Shift from baseline ²	Summary by laboratory category and parameter	End of Period	Shift analysis
	 Low, normal, and high categories 	within a Study	
	provided by the central laboratory	Part ²	
	• Parameters specified in Section 6.4.2.2		

¹ Pre-Amendment 3 Week 14 or End of Treatment within Pre-Amendment 3; Post-Amendment 3 Week 14 or End of Treatment within Post-Amendment 3

Laboratory assessments values meeting *any* of the PCS low or PCS high criteria specified in Section 6.4.2.1 will be identified as PCS in the laboratory data listing.

5.1.1.4.3.1 Potential Hy's Law

Potential Hy's Law criteria will be summarized by treatment group, double-blind treatment/oxybutynin chloride gel sequence, or oxybutynin chloride gel only group, as applicable, and visit for each open-label safety population as follows:

Table 5-18 Potential Hy's Law Summaries

Endpoint	Description	Timing	Methodology
Potential Hy's Law	Postbaseline assessment of the following	Study Period	Categorical
within 24-hour window	laboratory parameters based on blood draws	within Study Part ¹	descriptives
	collected within a 24-hour period:	, and the second	-
	• ALT or AST $\geq 3 \times ULN$ and		
	• TBL \geq 2 × ULN and		
	• $ALP < 2 \times ULN$		
Potential Hy's Law	Postbaseline assessment of the following	Study Period	Categorical

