5.2 Changes in the Conduct of the Study or Planned Analyses

At the time of writing this SAP, there were no changes in study conduct from what is described in the protocol and protocol amendments. Changes to planned analyses from what was described in the protocol are detailed in this SAP as described in Section 5.2.2 below.

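### SAP 5.1.1.4.2 replaces the protocol's lead-in split of Pre-Amendment 3 open-label adverse events with dose level and does not log it, so first-time and continuing gel users share one rate

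*SAP*

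**What the plan says.** Protocol 11.6.1 sets out the adverse-event presentation for each safety population. For the extension that followed the blinded phase it specifies "Pre-Amendment 3 open-label safety population: by treatment group in the lead-in double-blind period and overall". SAP 5.1.1.4.2 has instead "Pre-Amendment 3 open-label safety population: by oxybutynin chloride gel dose level and overall".

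For the pooled open-label set the two documents nearly agree: the protocol has "Combined open-label safety population: by oxybutynin chloride gel dose level and/or overall" and the SAP has "Combined open-label safety population: by oxybutynin chloride gel dose level and overall". Neither splits that set by lead-in.

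SAP 5.2 states: "Changes to planned analyses from what was described in the protocol are detailed in this SAP as described in Section 5.2.2 below". The log in 5.2.2 ends with version 2.0 of 28 March 2022. It records one adverse-event change, to the treatment-emergent definition in Table 5-15, and says nothing about the columns of the extension tables. The protocol text under review is Amendment 4, dated 31 October 2022, and still carries the lead-in split.

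The SAP keeps lead-in history for other safety data. Laboratory results are grouped by double-blind "treatment/oxybutynin chloride gel sequence, or oxybutynin chloride gel only group, as applicable, and by analyte and visit for each safety population". Potential Hy's Law cases and vital signs have the same sequence grouping.

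**The concern.** The Pre-Amendment 3 extension contains two kinds of patient. Those from placebo receive the study gel for the first time. Those from active treatment have already used it for 6 weeks. An adverse-event rate means something different in each: onset on first exposure in one, new onset during continued use in the other. The protocol kept them apart, and the SAP merges them without saying so.

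Three things are lost or blurred:

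- First-exposure events in former placebo patients appear in no adverse-event table of their own. The double-blind and Post-Amendment 3 tables describe other patients or, for the placebo group, another treatment.
- The single rate can lie below or above the first-exposure rate, and the planned columns do not let a reader tell which.
- Dose level does not stand in for lead-in. Protocol 9.4.1 says "All patients who entered the open-label safety period were started on 0.75 g/day oxybutynin chloride gel", so both histories begin at one level and can be found in every dose column. Dose is also adjusted after entry, partly in response to side effects.

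Safety in children is a secondary objective, and the extension was designed to supply longer-term safety data, so these tables will be read for that purpose.

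**Working it through.** **The plan's own figure.** There is none to reproduce: neither document states an expected adverse-event rate, overall or by lead-in group. The only quantified planning claim is power for the primary efficacy endpoint, which does not bear on this point. The check therefore has a textual part and an illustration.

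**Side by side (Pre-Amendment 3 extension)**

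| Output | Protocol | SAP |
|---|---|---|
| Adverse events | Lead-in group, overall (11.6.1) | Dose level, overall (5.1.1.4.2) |
| Laboratory | Sequence grouping (11.6.3) | Sequence grouping (5.1.1.4.3) |
| Vital signs | Sequence grouping (11.6.4) | Sequence grouping (5.1.1.4.4) |
| Change listed in SAP 5.2.2? | – | No |

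Of these outputs, only adverse events lose the lead-in history.

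**Who is counted, and for what**

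1. SAP Table 5-1 admits a patient to this population only after at least one open-label dose. Anyone who left during the blinded phase, including for an adverse event on gel, is absent.
2. Table 5-15 places an event in the open-label period by its start date, with the upper limit "event start date ≤ last dose date of open-label period + 30 days". An event that began on blinded gel and persists is counted in the double-blind period only.
3. The text above that table also treats an increase in intensity as treatment-emergent, but the period rule uses the start date alone.
4. Items 1 and 2 would tend to lower new-event rates in gel-experienced patients. Against that, everyone restarted at the same level, so a patient titrated up or down in the blinded phase changed dose on entry. The Pre-Amendment 3 schedule (SAP Appendix 1) then allows a further titration at Visit 7. New events in experienced patients are therefore quite possible.

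**Illustration.** Let p be the event rate in first-time gel patients, r × p the rate in gel-experienced patients, and w the experienced share of the population.

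Pooled rate = w × r × p + (1 − w) × p, so pooled ÷ first-time = w × r + (1 − w).

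Inputs: w = 0.5 follows from 1:1 randomisation if both groups continue equally (assumed). The values of r and p = 40% are assumed.

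| r | Ratio = 0.5r + 0.5 | Pooled rate if p = 40% | Error |
|---|---|---|---|
| 0.50 | 0.750 | 30% | 10 points low |
| 0.75 | 0.875 | 35% | 5 points low |
| 1.00 | 1.000 | 40% | none |
| 1.25 | 1.125 | 45% | 5 points high |

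If fewer gel patients continue, so that w = 0.45, the ratio at r = 0.50 is 0.45 × 0.50 + 0.55 = 0.775, and at r = 1.25 it is 0.45 × 1.25 + 0.55 = 1.113. The sign of the error depends only on whether r is below or above 1.

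**The case against.** The strongest reply is that this is one column change in a descriptive table, with no test or decision attached, and that first-exposure events are visible elsewhere. Much of that stands. The double-blind table by treatment group shows events from the first gel dose in the randomised gel patients, beside placebo, and includes those who stopped early. The Post-Amendment 3 table does the same for patients with no blinded lead-in. Erythema and anticholinergic symptoms have their own summaries, including gel summaries over the double-blind and open-label periods combined (SAP 5.1.1.4.6 and 5.1.1.5.1). Adverse events are also listed individually. None of this covers first-exposure adverse events in the former placebo patients as a group, which the protocol's split would have shown.

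A reader might go further and infer that the pooled rate understates adverse events on starting gel. The documents do not support that as a fact. It requires r below 1, no rates are given, and the common restart level leaves room for new events in experienced patients. The absence of blinded-phase dropouts is inherent in any extension and would remain after the split is restored.

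A reader might also take the pooled Pre- and Post-Amendment 3 open-label table as a second departure. It is not, because the protocol itself plans that table without a lead-in split. Nor did the protocol plan an adverse-event table counted from first gel dose over both periods.

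**Conclusion.** The discrepancy is certain from the text: the protocol's lead-in columns are replaced by dose level for one population's adverse-event tables, and the SAP's change log is silent. The two groups of patients then share one rate.

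The size of any error is unknown. Under equal lead-in groups and r between 0.5 and 1.25, the pooled rate is 0.75 to 1.125 times the first-exposure rate. Those limits are assumptions. Understatement is the more natural expectation, given who enters the population and how events are assigned to periods, but it is conditional.

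The effect is confined to the Pre-Amendment 3 open-label adverse-event tables as a departure from the protocol. No efficacy conclusion is touched. It merits correction because it is cheap, specific, and concerns a safety objective.

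**What to change.** - In SAP 5.1.1.4.2, restore three columns for the Pre-Amendment 3 open-label adverse-event tables: lead-in placebo, lead-in gel and overall. Dose level can be kept alongside.
- Record in SAP 5.2.2, with a reason, any departure from Protocol 11.6.1 that remains. Because the last logged SAP version predates Amendment 4, check the adverse-event section against the current protocol at the same time.
- Optional, beyond the protocol: one adverse-event summary counted from each patient's first gel dose across the double-blind and open-label periods, as already planned for erythema and anticholinergic symptoms.

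The cost is SAP wording and a few table columns from data already collected. The downside is small cells. Protocol 9.2 expected at least 25 evaluable patients to complete the extension; at that number an even split leaves 12 or 13 per lead-in column. Crossing lead-in with three dose levels would leave about 4 per cell (25 ÷ 6 = 4.2), so lead-in and dose are better shown as separate sets of columns than crossed.

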9.7.1.2 Severity Assessment

The investigator will provide an assessment of the severity of each AE by recording a severity rating on the appropriate page of the patient's eCRF. Severity, which is a description of the intensity of manifestation of the AE, is distinct from seriousness, which implies a patient outcome or AE-required treatment measure associated with a threat to life or functionality. Severity will be assessed according to the following scale:

Mild:	A type of AE that is usually transient and may require only minimal treatment or therapeutic intervention. The event does not generally interfere with usual activities of daily living.
Moderate:	A type of AE that is usually alleviated with additional specific therapeutic intervention. The event interferes with usual activities of daily living, causing discomfort but poses no significant or permanent risk of harm to the research participant.
Severe:	A type of AE that interrupts usual activities of daily living, or significantly

affects clinical status, or may require intensive therapeutic intervention.

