9.7.1.5 Immediate Reporting of Serious Adverse Events and Events of Special Interest

The Sponsor is required to inform worldwide regulatory authorities of SAEs that meet specific criteria. Therefore, the Sponsor must be notified immediately regarding any SAE that occurs after informed consent is obtained.

Within 24 hours of learning of any AE that meets one of the criteria for an SAE, the study site personnel must report the event to AbbVie Global Drug Safety on the SAE Form for Clinical Trials. The Sponsor's Study Physician may also be notified by telephone.

If, during follow-up, any nonserious AE worsens and eventually meets the criteria for an SAE, that AE should be recorded as a new SAE.

The site must transmit the SAE Form for Clinical Trials to the SAE fax number shown below. Even if an initial report is made by telephone, the SAE Form for Clinical Trials completed with all available details must still be faxed within 24 hours of knowledge of the event at the study site.

Supplemental information should be submitted as soon as available and may include laboratory results, radiology reports, progress notes, hospital admission and emergency room notes, holding and observation notes, discharge summaries, autopsy reports, and death certificates.

The investigator is expected to take all therapeutic measures necessary for resolution of the SAE. Any medications or procedures necessary for treatment of the SAE must be recorded on the appropriate pages of the patient's eCRF. All SAEs are to be followed by the study staff until resolution or until the SAE is deemed stable. The Sponsor may contact the study site to solicit additional information or follow up on the event.

Fax the SAE Form for Clinical Trials to AbbVie Inc.

Global fax number for SAE or Pregnancy Reporting: [name] (backup [contact]) or email it to [contact]. In case of fax failure or the site does not receive confirmation of receipt of the fax, the site must email the report to [contact].

Medical Emergency [contact]

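### SAP 5.1.1.4.2 counts worsening as treatment-emergent in its text, but the period windows in Table 5-15 use event start date only, so some worsening on treatment falls outside the adverse event tables

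*SAP*

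**What the plan says.** SAP 5.1.1.4.2 defines a treatment-emergent AE twice. The running text includes an AE if "the AE initially occurs or increases in intensity on or after the first dose of study drug in the study", and excludes events that occur more than 30 days after the last dose.

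Table 5-15 then gives a window for each period. For a double-blind participant who continues, it is "First dose date of double-blind period ≤ event start date < first dose date of open-label period if participant enters the 8-week open-label period". For the open-label period it is "First start date of open-label period ≤ event start date ≤ last dose date of open-label period + 30 days". Neither window mentions intensity, and the SAP does not say whether the text or the table governs. The change log in SAP 5.2.2 records that version 2.0 revised the double-blind window; it mentions no worsening rule.

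The AE summaries in Table 5-16 are produced by study period within study part, and for the combined open-label period. One listed grouping is "Pre-Amendment 3 open-label safety population: by oxybutynin chloride gel dose level and overall". The severity tables have "Participants categorized overall and within each SOC and PT for the most intense occurrence".

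On recording, Protocol 9.7.1.2 has the investigator assess each AE by "recording a severity rating on the appropriate page". Protocol 9.7.1.5 says that if "any nonserious AE worsens and eventually meets the criteria for an SAE, that AE should be recorded as a new SAE". Protocol 9.7.1 starts AE collection at signature of the consent form, before any dose. Protocol 9.4.1 states that "all patients received oxybutynin chloride gel during the 8-week open-label treatment period".

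**The concern.** The summaries are by period, so the windows in Table 5-15 decide what is counted. A programmer who follows the table drops every event that qualifies only through worsening, although the text says such events count. Two programmers reading the same section could produce different tables.

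Two groups of events are affected. The first is AEs that begin after consent but before the first dose and become worse on treatment. The second is AEs that begin on double-blind placebo and become worse after the switch to gel. For the second group, onset under placebo is correctly counted there; what is lost is the later worsening on gel.

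Safety is a secondary objective (Protocol 8.2), and the open-label extension was meant to produce long-term safety data (Protocol 9.2). Anticholinergic symptoms are graded on a questionnaire, and AEs detected there go on the AE form (Protocol 9.8.5), so a symptom that is mild at first and later worse is a plausible pattern.

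**Working it through.** The plan gives no figure to reproduce, so the check is to run test events through both definitions.

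**Inputs.** The two windows and the text rule come from SAP 5.1.1.4.2. Durations are 6 weeks double-blind (6 × 7 = 42 days) and 8 weeks open-label (8 × 7 = 56 days). I assume for illustration that every dose is taken and there is no gap: double-blind days 1 to 42, open-label days 43 to 98 (42 + 56 = 98). The open-label window closes at 98 + 30 = day 128.

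**Rules, for a participant who enters open-label.**
- Text: treatment-emergent if onset or worsening is on or after day 1.
- Table, double-blind: 1 ≤ start < 43.
- Table, open-label: 43 ≤ start ≤ 128.

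| Test event | Text | Double-blind window | Open-label window |
|---|---|---|---|
| A. Starts day −5, worsens day 20 | Yes | −5 < 1: no | −5 < 43: no |
| B. Starts day −5, worsens day 60 | Yes | −5 < 1: no | −5 < 43: no |
| C. Starts day 20 on placebo, worsens day 60 on gel, one record | Yes, from onset | 1 ≤ 20 < 43: yes | 20 < 43: no |
| D. Worsening entered as a new record starting day 60 | Yes | 60 ≥ 43: no | 43 ≤ 60 ≤ 128: yes |

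**Post-Amendment 3.** There is one open-label period of 14 × 7 = 98 days, so the window is 1 ≤ start ≤ 128. An event starting on day −5 and worsening on day 20 is treatment-emergent by the text; by the table −5 < 1, so it is not counted.

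**Reading the results.** A, B and the Post-Amendment 3 event are direct contradictions between text and table. C is different. The text is anchored to the first dose in the study, which for a placebo patient is the first placebo dose, so C is treatment-emergent under both definitions and the text does not assign the worsening to gel. C exposes a gap in the table, which has no worsening rule for each period. D shows that the table works if worsening always creates a new record dated at the worsening.

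**Is a new record assured?** The protocol states one on worsening only when a nonserious AE becomes serious (9.7.1.5). Grade 3 erythema is also to be recorded as an AE (9.7.3). No general rule covers other nonserious worsening. Protocol 12 refers to sponsor instructions for completing the eCRF, which are not among the documents.

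**Severity tables.** Table 5-16 takes the worst occurrence and does not say that the intensity must have been reached within the period being summarized. If event C is held as one record carrying its worst grade, the grade reached on gel would appear under double-blind placebo. This is conditional on how the record is kept.

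**The case against.** The strongest reply is that assigning an event to the period in which it began is an ordinary convention, and that the text never promised to move later worsening to gel. That is right for event C, which is why it is described as a gap and not as a contradiction. It does not answer A and B, where the SAP's own worsening clause has no effect in the table.

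A second reply is that data entry takes care of it. Protocol 9.7.1 lists a change in severity of a pre-existing disease among its examples of AEs, so worsening of a condition that predates consent is an AE in its own right. Clinically significant laboratory changes (9.7.2), Grade 3 erythema and other clinically significant skin problems (9.7.3), and anticholinergic AEs found on the questionnaire (9.8.5) also go on the form. These routes narrow the problem. They do not say how worsening of an AE already on the form is entered. The unseen eCRF instructions may say so; if they do, the SAP should state that Table 5-15 depends on them.

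Third, few pre-dose AEs may exist, because both schedules of events mark AE assessment only from the first visit after dosing begins. Against that, collection formally runs from consent, and SAP Table 6-8 gives an imputation rule for AEs in the screening period, so such records are expected.

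Fourth, worsening may show elsewhere: questionnaire shift tables, erythema by visit and the listings of all AEs. This is true, but none of these is a treatment-emergent AE count.

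Fifth, the placebo-to-gel crossover concerns Pre-Amendment 3 patients only, enrolled under earlier protocol versions whose AE text is not supplied. This stands, and it limits what can be said about how their worsening was recorded.

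**Conclusion.** The definitions in SAP 5.1.1.4.2 need to be reconciled. The direct conflict is the AE that starts between consent and first dose and worsens on treatment: counted by the text, in no period by the table, in both study parts. The related gap is nonserious worsening on open-label gel of an AE that began on double-blind placebo, which is not counted in the open-label gel tables unless it was entered as a new record.

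The size cannot be computed. The documents give no AE counts, no rate of worsening, and no number of placebo patients who continued to gel. A reader might apply assumed rates to the 48 patients per arm in the sample size section, but that is the planned arm of a design later replaced by open-label enrollment, so the result would be only an assumption.

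A reader might also infer that worsening on gel is always charged to placebo and never to gel, for every former placebo patient, so that gel harm is understated on both sides. The documents do not support that. Worsening to a serious AE calls for a new record, and severe erythema may produce one; either would count under gel if dated at the worsening. Table 5-15 has a branch for participants who do not enter open-label. The display of gel severity under placebo depends on one record carrying the worst grade.

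This is a minor point of specification that can change treatment-emergent AE counts and is worth settling before database lock.

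**What to change.** 1. In each window of Table 5-15, replace the event start date by the event start date or the date of increase in intensity. With the test days above, A then counts in the double-blind period, B in the open-label period, and C in both: onset under placebo, worsening under gel.
2. In the severity tables, use the intensity reached within the period being summarized.
3. State how the date of worsening is obtained: a new record at each increase in intensity, or an intensity-change date on the existing record. Where earlier records hold no such date, state that as a limitation.

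The cost is an edit to one table, a sentence in the severity specification and a statement on data source. A new eCRF instruction would help only data still to be collected; it cannot create worsening dates for Pre-Amendment 3 patients, whose crossover the protocol describes as past. Recovering those dates could require retrospective queries, and the limitation statement is the alternative. The downside is that a few events will appear in two periods at different intensities, which a table footnote should explain.
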